3.4.1 Primary Exposure

Chemical power calculated according to Lilien et al. [Lilien et al. 2023]:

Step 1: Estimation of local superoxide (O_2^-) production ($Pulm_{ROS}$) from lung oxygen consumption as a function of F_iO_2

$$Pulm_{ROS} = 1.7 * 10^{-5} + ((F_iO_2 - 0.21) * 1.63 * 10^{-4}) \text{ (mol/min)}$$

Step 2: Calculate chemical power (CP) from step 1 based on the first electron affinity of oxygen (141 kJ/mol).

$$CP = 141000 * Pulm_{ROS} \text{ (J/min)}$$

3.4.2 Secondary Exposure

Since plateau pressure was not recorded in every patient, dynamic driving pressure will be calculated as peak pressure – PEEP and dynamic mechanical power will be calculated according to the following formula:

$$MP = 0.098 * Vt * RR * (Ppeak - 0.5 * \Delta P_{insp})$$

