2.2 Secondary Aims & Hypotheses

Secondary Aim 1: To identify the thresholds of harm for the associations of intraoperative chemical and mechanical power with postoperative pulmonary complications within seven days after surgery.

Secondary Hypothesis 1: The exposures to intraoperative chemical and mechanical power have thresholds of harm (inflection points) from which on the risk for postoperative pulmonary complications within seven days after surgery increases substantially.

Secondary Aim 2: To evaluate the interaction between the intraoperatively applied chemical and mechanical power on postoperative pulmonary complications within seven days after surgery.

Secondary Hypothesis 2: Chemical power-related harm largely depends on the concomitantly applied mechanical power, meaning that chemical power causes significantly more postoperative pulmonary complications within seven days after surgery when exposed to high intraoperative mechanical power.

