3.6 Statistical Analysis

3.6.1 Descriptive statistics

The following variables will be descriptively presented, and additionally grouped by low, moderate, marked, and substantial chemical power (<25%, 25–50%, 50–75%, and 75–100% quantile of mechanical power), and considered as potential confounders (*) for the inferential statistics. Mean (standard deviation), median (interquartile range), frequency (percentage) will be reported based on variable type

and distribution.

Demographics

- Age *
- Sex *
- Height (cm)
- Weight (kg)
- BMI (kg/m^2) *
- ASA physical status *
- Trial *

Respiratory risk factors

- ARISCAT score *
- Preoperative SpO₂ *
- Respiratory infection within the past month *
- Anemia *

Coexisting conditions

- Heart failure *
- Chronic obstructive pulmonary disease *
- Cancer *

Surgery characteristics

- Preoperative hemoglobin (g/dL) *
- Type of surgery (abdominal versus non-abdominal) *
- Specific procedure
- Surgical approach (laparoscopic versus non-laparoscopic) *
- Year of surgery *
- Emergency or elective procedure *
- Duration of surgery *

Intraoperative mechanical ventilation parameters

- Tidal volume (V_t)
- Respiratory rate (RR)
- Peak pressure (P_{insp})
- Driving pressure (ΔP_{insp})
- Inspiratory oxygen fraction (FiO₂)
- Positive end-expiratory pressure (PEEP) *
- Exposures: chemical power and mechanical power
- Ventilation mode (VCV vs. PCV)

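### One mechanical power formula serves both volume and pressure control, so the MP threshold and quartiles may be biased to an extent set by the unreported share of pressure control

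*Combined protocol and SAP*

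**What the plan says.** Section 3.4.2 explains the use of a dynamic measure by data availability: "Since plateau pressure was not recorded in every patient". It then sets the driving pressure ("dynamic driving pressure will be calculated as peak pressure – PEEP") and says that "dynamic mechanical power will be calculated according to the following formula", followed by one expression, beginning "MP = 0.098 * Vt * RR * (Ppeak - 0.5" and completed by the driving pressure term. Mode is not mentioned there.

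Section 3.6.1 lists "Ventilation mode (VCV vs. PCV") among the intraoperative variables, so both modes are expected. The item has no asterisk. Asterisked variables are those "considered as potential confounders (*) for the inferential statistics"; Trial and "Positive end-expiratory pressure (PEEP") carry one.

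Secondary aim 1 in section 2.2 is "To identify the thresholds of harm for the associations of intraoperative chemical and mechanical power with postoperative pulmonary complications". Section 3.6.2 pursues it with splines and threshold regression, and the primary model gives odds ratios per unit of MP. Sections 3.6.1 and 3.6.3 use quartiles of MP. No mode-specific MP, mode stratum or related sensitivity analysis is planned, and section 3.6.5 does not list the issue as a limitation.

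**The concern.** Work per breath is the integral of pressure over volume. A formula that assumes a linear pressure rise suits constant-flow volume control with little resistive pressure. In pressure control the airway pressure is held near its peak for most of inspiration, so the same recorded pressures represent more work. The same calculated MP can then stand for different energy in the two modes.

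This matters most where the J/min value is itself the result. A harm threshold estimated over two scales may describe neither mode. Patients may also be placed in the wrong MP quartile or in the wrong MP stratum of secondary aim 2.

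**Working it through.** The documents give no MP value, PCV share or ventilator settings, so there is no plan figure to reproduce. Only the formula and the driving pressure definition come from section 3.4.2. All settings below are assumptions.

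**1. The plan's formula after substitution.** With ΔP = Ppeak − PEEP, the bracket is Ppeak − 0.5(Ppeak − PEEP) = (Ppeak + PEEP)/2.

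**2. Pressure control.** At constant inspiratory pressure, work per breath is Ppeak × Vt. The plan's value as a share of this is (Ppeak + PEEP)/(2 Ppeak).

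| PEEP | ΔP | Ppeak | Share | Understatement |
|---|---|---|---|---|
| 2 | 16 | 18 | 20/36 = 0.56 | 44% |
| 5 | 14 | 19 | 24/38 = 0.63 | 37% |
| 12 | 12 | 24 | 36/48 = 0.75 | 25% |

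For the middle row with Vt 0.5 L and RR 12, 0.098 × 0.5 × 12 = 0.588. The plan gives 0.588 × 12 = 7.1 J/min and constant pressure gives 0.588 × 19 = 11.2 J/min. A numerical resistance–compliance model at PEEP 4 and Ppeak 20 gives a share of 0.60 with instantaneous rise and 0.62 to 0.66 with rise times of 0.1 to 0.3 s.

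**3. Volume control.** At constant flow with resistive gap r = Ppeak − Pplat, mean inspiratory pressure is Ppeak − 0.5(Pplat − PEEP) = (Ppeak + PEEP)/2 + r/2. At PEEP 5 and Ppeak 19, the share is 12/13 = 0.92 for r = 2 and 12/15 = 0.80 for r = 6, so VCV is 8% to 20% low.

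**4. Between modes.** PCV relative to VCV is 0.63/0.92 = 0.68 to 0.63/0.80 = 0.79, that is 32% to 21% low, against 37% for the PCV error alone. The formula omits ΔP/2 in PCV and r/2 in VCV.

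**5. Threshold.** Simulated hinge logistic regression: n = 3,000, 40 replicates, true threshold 10 J/min, PEEP centred on 4 or 12, mean ΔP 14, constant pressure in PCV and no resistive gap in VCV.

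| PCV share | Mean estimate | SD across replicates | With mode covariate |
|---|---|---|---|
| 0% | 9.8 | 0.7 | 9.8 |
| 5% | 9.8 | 0.6 | 9.8 |
| 10% | 9.5 | 0.8 | 9.5 |
| 25% | 8.3 | 1.0 | 8.3 |
| 50% | 7.0 | 0.9 | 7.1 |

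A second simulation (n = 200,000, true threshold 12) gave 11.5, 10.5 and 9.5 at 10%, 30% and 50% PCV, with the pooled slope changing by about 2% to 10%.

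**6. Quartiles.** With constant pressure in PCV and no resistive gap in VCV, 14% to 43% of patients fall in the wrong MP quartile as the PCV share goes from 10% to 50%. With a 4 cmH2O gap and PCV work at 93% of Ppeak × Vt, the figures are 9.8%, 19.4% and 25.2% at 10%, 30% and 50% PCV.

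**The case against.** The plan labels its measure dynamic and gives a reason, so this is a declared surrogate. The threshold is a secondary aim, much of the quartile use is descriptive, and the pooled slope moves little. These points stand and limit the weight of the concern. The stated reason, however, concerns missing plateau pressure and does not address mode.

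A reader might infer that the threshold is shifted. The documents do not support that as a fact, because they do not give the PCV share. At 10% PCV the shift from the 0% case is 9.8 − 9.5 = 0.3 J/min, against a replicate SD of 0.8.

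A reader might also infer that the fault is the missing adjustment for mode. It is not. The PCV error is proportional to ΔP, so a mode main effect cannot remove it, and in the simulation the covariate left the threshold essentially unchanged. For the same reason, the asterisk on Trial may absorb differences in baseline risk but not the exposure error. Nor would an asterisk secure a place in the model, since section 3.6.2 allows a variable to be dropped when it changes both exposure coefficients by less than 10%.

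The strongest objection is that a formula split does not put the modes on one scale. With a 4 cmH2O gap and PCV work at 93% of Ppeak × Vt, it lowers the wrong-quartile share only from 9.8% to 8.7%, 19.4% to 17.6% and 25.2% to 20.8% at 10%, 30% and 50% PCV. The arithmetic at PEEP 5 and Ppeak 19 shows why. PCV work is then 0.93 × 19 = 17.7 cmH2O per unit volume: the plan is 5.7 too low and Ppeak × Vt is 1.3 too high. VCV is r/2 too low either way. The mismatch between modes is 5.7 − r/2 under the plan and 1.3 + r/2 after the split: 4.7 against 2.3 at r = 2, 3.7 against 3.3 at r = 4, and 2.7 against 4.3 at r = 6. So the split helps clearly at small gaps and can hurt at large gaps with slow pressure rise.

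**Conclusion.** The concern holds in a limited form. One formula is applied to two modes that the plan itself distinguishes, and nothing in the plan corrects or examines this. PCV work is understated by about 25% to 44% at the assumed settings under constant pressure, less with a slow rise. VCV is understated by about 8% to 20% at the central setting.

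The MP threshold and quartiles may be biased as a result. On the simulated assumptions the threshold bias is negligible at about 10% PCV or less and potentially material from about 25%. Those simulations assume constant pressure in PCV and no resistive gap in VCV, so they show the largest contrast between modes. The effect on the pooled slope, and so on the MP side of the primary comparison, is smaller. The documents do not support a stronger reading that the threshold or the primary result is known to be wrong.

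**What to change.** 1. Report the share of patients, or of ventilated hours if mode was recorded hourly, in PCV, overall and by trial.
2. Calculate hourly MP by mode: the stated formula in VCV and 0.098 × Vt × RR × Ppeak in PCV. Alternatively, keep the single formula as primary and prespecify the mode-specific version as a sensitivity analysis.
3. Report the MP threshold by mode, or in VCV patients only. This avoids mixing the scales whatever the resistive gap.
4. Where plateau pressure was recorded, repeat the VCV analysis with plateau-based driving pressure. The documents do not say how many patients have it or whether whole trials lack it, so state that number.
5. Do not present mode as a covariate as the correction.

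The cost is SAP wording and a little code, since mode and the pressures are already listed in section 3.6.1. The choice should be fixed before the threshold is estimated. There are downsides: the PCV formula overestimates work when pressure rises slowly, VCV still omits part of the resistive pressure so the modes are not on an identical scale, and stratified threshold estimates are less precise.

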3.5 Outcome

3.5.1 Primary Outcome

Collapsed composite outcome of postoperative pulmonary complications (PPCs) during the first seven postoperative days according to the definitions of the underlying studies presented in table 1.

Table 1. Definitions of postoperative pulmonary complications.

	PROVHILO	iPROVE	PROBESE
Mild respiratory failure	PaO ₂ < 60 mmHg or SpO ₂ < 90% breathing at least 10 minutes of room air but responding to supplemental oxygen of 2 L/minute	SpO ₂ < 92% with FiO ₂ of 0.21 or SpO ₂ < 95% with FiO ₂ of 0.50	PaO ₂ < 60 mmHg or SpO ₂ < 90% breathing at least 10 minutes of room air but responding to supplemental oxygen of 2 L/minute
Severe respiratory failure	PaO ₂ < 60 mmHg or SpO ₂ < 90% breathing ≥ 10 minutes of room air but responding only to supplemental oxygen > 2 L/minute or need for noninvasive or invasive mechanical ventilation	Increased FiO ₂ , increased requirement for CPAP, or the need for noninvasive or invasive ventilation	PaO ₂ < 60 mmHg or SpO ₂ < 90% breathing ≥ 10 minutes of room air but responding only to supplemental oxygen > 2 L/minute or need for noninvasive or invasive mechanical ventilation
ARDS	AECC criteria*	Berlin criteria**	Berlin criteria**
Pulmonary infection	Need of antibiotics and at least one of the following criteria: new or changed sputum, new or changed lung opacities on chest X-ray when clinically indicated, tympanic temperature >38.3°C, WBC count >12,000/µl in the absence of other infectious focus	Presence of a new pulmonary infiltrate and/or progression of previous pulmonary infiltrates on a chest radiograph plus at least two of the following criteria: (a) leukocytosis with > 12,000 WBC/mm ³ or leukopenia with < 4000 WBC/mm ³ , (b) fever > 38.5°C or hypothermia < 36°C, and (c) increased secretions with purulent sputum and a positive bronchial aspirate	Presence of a new pulmonary infiltrate and/or progression of previous pulmonary infiltrates on a chest radiograph plus at least two of the following criteria: (a) leukocytosis with > 12,000 WBC/mm ³ or leukopenia with < 4000 WBC/mm ³ , (b) fever > 38.5°C or hypothermia < 36°C, and (c) increased secretions with purulent sputum and a positive bronchial aspirate
Pleural effusion	Chest radiography with the presence of costophrenic angle blunting, displacement of adjacent anatomical structures, and blunting of the hemidiaphragmatic silhouette in the supine position	Chest radiography with the presence of costophrenic angle blunting, displacement of adjacent anatomical structures, and blunting of the hemidiaphragmatic silhouette in the supine position	Chest radiography with the presence of costophrenic angle blunting, displacement of adjacent anatomical structures, and blunting of the hemidiaphragmatic silhouette in the supine position
Atelectasis	Chest radiography with lung opacification with shift of the mediastinum, hilum, or hemidiaphragm towards the affected area, and compensatory overinflation in the adjacent non-atelectatic lung	Combination of SpO ₂ ≤ 96% during the air test and chest radiography with lung opacification with shift of the mediastinum, hilum, or hemidiaphragm towards the affected area, and compensatory overinflation in the adjacent non-atelectatic lung	Chest radiography with lung opacification with shift of the mediastinum, hilum, or hemidiaphragm towards the affected area, and compensatory overinflation in the adjacent non-atelectatic lung
Pneumothorax	Chest radiography with air in the pleural space with no vascular bed surrounding the visceral pleura	Chest radiography with air in the pleural space with no vascular bed surrounding the visceral pleura	Chest radiography with air in the pleural space with no vascular bed surrounding the visceral pleura
Bronchospasm	Presence of expiratory wheezing treated with bronchodilator	Presence of expiratory wheezing treated with bronchodilator	Presence of expiratory wheezing

ARDS: Acute Respiratory Distress Syndrome; SIRS: systemic inflammatory response syndrome; AECC: American–European consensus conference; WBC: White blood cells; PaO₂: Arterial oxygen pressure; SpO₂: peripheral oxygen saturation; FiO₂: inspired oxygen fraction.

3.6 Statistical Analysis

3.6.1 Descriptive statistics

The following variables will be descriptively presented, and additionally grouped by low, moderate, marked, and substantial chemical power (<25%, 25–50%, 50–75%, and 75–100% quantile of mechanical power), and considered as potential confounders (*) for the inferential statistics. Mean (standard deviation), median (interquartile range), frequency (percentage) will be reported based on variable type

and distribution.

Demographics

- Age *
- Sex *
- Height (cm)
- Weight (kg)
- BMI (kg/m^2) *
- ASA physical status *
- Trial *

Respiratory risk factors

- ARISCAT score *
- Preoperative SpO₂ *
- Respiratory infection within the past month *
- Anemia *

Coexisting conditions

- Heart failure *
- Chronic obstructive pulmonary disease *
- Cancer *

Surgery characteristics

- Preoperative hemoglobin (g/dL) *
- Type of surgery (abdominal versus non-abdominal) *
- Specific procedure
- Surgical approach (laparoscopic versus non-laparoscopic) *
- Year of surgery *
- Emergency or elective procedure *
- Duration of surgery *

Intraoperative mechanical ventilation parameters

- Tidal volume (V_t)
- Respiratory rate (RR)
- Peak pressure (P_{insp})
- Driving pressure (ΔP_{insp})
- Inspiratory oxygen fraction (FiO₂)
- Positive end-expiratory pressure (PEEP) *
- Exposures: chemical power and mechanical power
- Ventilation mode (VCV vs. PCV)

3.6.2 Inferential statistics

Primary aim:

We will summarize intraoperative chemical and mechanical power by calculating time-weighted averages for each patient. The influence of the intraoperatively applied time-weighted average chemical and mechanical power on composite postoperative pulmonary complications will be evaluated by multivariable logistic regression – estimating the odds ratios related to the effect of 1 unit increase in chemical or mechanical power. The regression model will be calculated with and without the above-mentioned confounders. We will consider the exclusion of a potential confounder if its inclusion results in a change in the regression coefficients (beta) for both exposures of less than 10%.

Secondary aim 1:

The relationship between varying levels of chemical / mechanical power and postoperative pulmonary complications will be analysed via multivariable logistic regression including cubic splines with up to five knots of chemical and mechanical power. We will further evaluate whether chemical and mechanical power have an upper threshold of harm, whereafter the odds for PPCs increase substantially by means of threshold regression. We will consider a 5% change in slope as clinically relevant, although there is no established minimal clinically important difference for PPCs, and this definition remains arbitrary.

Secondary aim 2:

We will evaluate the interaction between chemical power and mechanical power by implementing an interaction term for the intraoperatively applied time-weighted average mechanical power in the multivariable regression model performed to evaluate the primary aim. Additionally, we will analyse the effect of chemical and mechanical power on PPCs for 5 subsets of the study population stratified by chemical or mechanical power for each of the following patterns: 1) increasing chemical power and matched mechanical power, 2) matched chemical power and increasing mechanical power, 3) increasing chemical power and decreasing mechanical power, and 4) increasing chemical power and increasing mechanical power. Data will also be graphically presented with a 3D surface plot showing chemical and mechanical power on the x- and z-axes and the percentage of PPCs on the y-axis. Therefore, the population will be divided into equally sized groups including an certain fraction of patients of the ranges of both exposures.

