3. METHODS

3.1 Study Design and Population

We will perform a post hoc analysis of the previously combined dataset named 'Re-evaluation of the Effects of High PEEP with Recruitment Manoeuvres versus Low PEEP without Recruitment Manoeuvres During General Anaesthesia for Surgery' (REPEAT), registered at ClinicalTrials.gov: NCT03937375 on 3rd May 2019. This dataset merged the individual patient data from three RCTs, the 'High versus low positive end-expiratory pressure during general anesthesia for open abdominal surgery' (PROVHILO) study (registered with Controlled-Trials.com: ISRCTN70332574), the 'Individualized perioperative open-lung approach versus standard protective ventilation in abdominal surgery' (iPROVE) study (registered with ClinicalTrials.gov: NCT02158923) and the 'Effect of intraoperative high positive end-expiratory pressure with recruitment manoeuvres vs low PEEP on postoperative pulmonary complications in obese patients' (PROBESE) study (registered with ClinicalTrials.gov: NCT02148692).

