3.6.4 Sample size considerations

We do not perform a formal power calculation; instead, the available number of patients in the pooled dataset serves as the sample size.

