3.6.5 Limitations

We are aware of several limitations of our analyzes. (1) Although the database was derived from trials, our study is observational, meaning we may detect associations but not establish causality. (2) Due to a widespread use of lung-protective mechanical ventilation exposure to higher ranges of mechanical power is presumably rare. (3) The use of supplemental oxygen (FiO₂) is potentially highly confounded by underlying pulmonary risk and patients' intraoperative responses to surgery and mechanical ventilation. (4) The underlying trials used slightly different definitions of postoperative pulmonary complications, adding further variability and potential bias to the results.

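### The pooled logistic models ignore centre, and Trial, the only grouping variable, is absent from the unadjusted model and can be dropped; odds ratios may be biased and intervals may be too narrow

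*Combined protocol and SAP*

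**What the plan says.** Section 3.1 describes the source: "This dataset merged the individual patient data from three RCTs". Section 3.6.2 states that the association of the two time-weighted powers with the composite outcome "will be evaluated by multivariable logistic regression". Secondary aim 1 uses the same type of model with cubic splines, followed by threshold regression. Secondary aim 2 adds an interaction term to the primary model.

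Section 3.6.1 stars the variables that are "considered as potential confounders (*) for the inferential statistics". Trial is starred. Hospital, centre or site is not on the list, starred or not. No random effect, generalised estimating equation, stratification or cluster-robust variance appears anywhere.

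On covariates, Section 3.6.2 says: "The regression model will be calculated with and without the above-mentioned confounders". It then allows a confounder to be left out if including it moves the coefficients of both exposures by less than 10%. Trial is not exempted.

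Section 3.6.5 concedes: "The underlying trials used slightly different definitions of postoperative pulmonary complications, adding further variability and potential bias to the results". It does not mention clustering.

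**The concern.** Two separate problems follow from how the grouping is handled.

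**Bias at trial level.** Table 1 in Section 3.5.1 shows that a complication in one trial need not count in another. The saturation limits for mild respiratory failure differ, atelectasis in iPROVE also needs a saturation criterion, ARDS follows one of two consensus definitions, and bronchospasm must have been treated in two trials but not in the third. Baseline PPC risk can therefore differ by trial for reasons of definition alone. If oxygen fraction or ventilator settings also differ by trial, a model without Trial attributes part of that difference to chemical or mechanical power.

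**Dependence and confounding at centre level.** Chemical power is a function of inspired oxygen fraction alone (Section 3.4.1). Mechanical power uses tidal volume, respiratory rate and pressures (Section 3.4.2). Such settings can follow local habit. Several outcome components need a chest film, and one pulmonary infection definition takes the film only when clinically indicated, so detection can also be local. If exposure and outcome both share a centre component, a single-level model understates the standard errors, and differences in centre practice can also confound the odds ratios.

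The primary hypothesis compares the contributions of the two powers, so unequal distortion of their coefficients would bear directly on it.

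**Working it through.** **No figure to reproduce.** The plan gives no sample size, event count or alpha, and says: "We do not perform a formal power calculation". It mentions a 95% interval only for the relative risks in Figure 4. The number of centres, patients per centre (m) and both ICCs are not in the documents. Every input below is assumed.

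**Step 1: design effect for a patient-level exposure (Moulton form).**

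- DE = 1 + (m − 1) × ICC of exposure × residual ICC of outcome
- Correct SE ÷ reported SE = √DE
- True size of a nominal 5% test = 2 × [1 − Φ(1.96/√DE)]

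| m | ICC exposure | ICC outcome | DE | SE ratio | True size |
|---|---|---|---|---|---|
| 30 | 0.2 | 0.02 | 1 + 29 × 0.004 = 1.116 | 1.06 | 6% |
| 30 | 0.5 | 0.10 | 1 + 29 × 0.05 = 2.45 | 1.57 | 21% |
| 10 | 0.2 | 0.02 | 1 + 9 × 0.004 = 1.036 | 1.02 | 5% |
| 10 | 0.5 | 0.10 | 1 + 9 × 0.05 = 1.45 | 1.20 | 10% |
| 10 | 0.05 | 0.01 | 1 + 9 × 0.0005 = 1.0045 | 1.00 | 5% |
| 40 | 0.3 | 0.05 | 1 + 39 × 0.015 = 1.585 | 1.26 | 12% |
| 80 | 0.6 | 0.10 | 1 + 79 × 0.06 = 5.74 | 2.40 | 41% |

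At m = 30 the correct SE is 6% to 57% larger than the reported one. Put the other way, the reported SE is 1 − 1/1.06 ≈ 5% to 1 − 1/1.57 ≈ 36% too small. The last three rows show how wide the range becomes if the assumptions are relaxed.

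**Step 2: does Trial as a covariate repair this?** A null simulation used 60 centres of 40 patients in three trials, with 400 runs per scenario. Exposure means differed by −0.5, 0 and +0.5 SD between trials. The outcome ICC was set on the logit scale. Entries are the percentage of runs that rejected a true null at 5%; the Monte Carlo error is about 1 to 2 points for entries up to 26%.

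| ICC exposure, ICC outcome | Trial log-odds shift | No Trial | Trial | Trial, clustered SE | Centre fixed effects |
|---|---|---|---|---|---|
| 0.05, 0.01 | none | 6.5 | 6.2 | 5.2 | 5.0 |
| 0.3, 0.05 | none | 11.3 | 11.5 | 7.5 | 5.2 |
| 0.6, 0.10 | none | 26.0 | 23.0 | 8.0 | 4.0 |
| 0.3, 0.05 | −0.5, 0, +0.5 | 84.8 | 9.5 | 6.0 | 7.2 |
| 0.3, 0 | −0.5, 0, +0.5 | 89.7 | 5.8 | 6.2 | 5.8 |

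The last row isolates the trial level. Without Trial the model is badly biased; with Trial it is near nominal. The second and third rows isolate the centre level. Trial does not help there, and clustered SEs or centre fixed effects do.

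**Step 3: what the 10% rule permits.** A single removal may shift each exposure coefficient by just under 10%. If the two move in opposite directions, their ratio can change by a factor of up to about 1.1/0.9 = 1.22, and the primary aim concerns their relative size. The rule looks only at coefficients, so it gives no protection to a grouping variable that matters for the variance.

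**The case against.** A reader might infer that the intervals are too narrow as a matter of fact. The documents do not support that. It requires positive within-centre correlation of both exposure and outcome, and enough patients per centre. None of these is given, and the assumed range includes no effect at all. The outcome ICC that counts is the residual one, after surgery type, approach, year, ARISCAT score and the other starred covariates, and it may be smaller than a crude value.

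A reader might also infer that the plan ignores the trial level. It does not: Trial is a starred candidate. The 10% rule would normally keep Trial where it confounds strongly, because the coefficients would then move by more than 10%. The rejection rates near 90% therefore illustrate the model without confounders under invented trial differences. They are not an error rate for this study.

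The influence of local practice is inferred too. The plan's own account of oxygen fraction is that it "is potentially highly confounded by underlying pulmonary risk" and by patients' responses during surgery. The trials were designed around ventilator settings, especially PEEP, and PEEP is a starred covariate, so allocation may explain part of mechanical power. Finally, the plan states no alpha and judges thresholds by a 5% change in slope, so interval coverage is a better measure here than test size.

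All of this limits the size of the claim. What stands is that no model accounts for centre, that Trial is certain to be missing from one model and removable from the others, and that the listed limitations do not mention clustering.

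**Conclusion.** The point holds in conditional form. Trial is left out of the unadjusted model and is not protected in the adjusted ones. Because outcome definitions differ by trial, omitting it can bias the exposure odds ratios. This part rests on the plan's own text and on the possibility that exposure levels differ by trial.

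The centre part rests on assumptions. If exposure and residual outcome both cluster by centre, intervals may be too narrow, by the amounts in the first two rows of the design-effect table for 30 patients per centre and by much less for 10. With weak clustering there is nothing to correct. Adjusting for Trial alone would not remove a centre effect where one exists.

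**What to change.** - Keep Trial as a fixed effect in every model and exempt it from the 10% rule. Replace the model without confounders by a minimally adjusted one that still contains Trial.
- State whether the pooled file holds a centre code. If it does, add a centre effect to the primary, spline, threshold and interaction models, either fixed or as a random intercept nested in Trial. This addresses confounding and dependence together. A random intercept assumes that centre effects are unrelated to exposure, so it removes centre-level confounding only in part; fixed effects go further.
- Use cluster-robust standard errors by centre only as a fallback. They correct interval width and leave the odds ratios as they are.
- Treat the relative-risk intervals in Figure 4 in the same way.
- If no centre code exists, say so in Section 3.6.5.

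The cost is one model term or variance option. The downside is slightly wider intervals, and more than slightly with fixed effects if much of the exposure variation lies between centres.
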